6.1 Inclusion Criteria

Participants are eligible for inclusion in the study only if they meet all of the following criteria at screening. The timeframes included in the following criteria are relative to screening unless otherwise noted.

1. Aged 18 to 65 years, inclusive.

Part A Cohorts through 100 mg:

2. Healthy male participants (including self-reported surgically sterile males), as determined through medical history and physical examination, must agree to the following:
 - a. When engaging in sex with a WOCBP, both the male participant and his female partner must use highly effective contraception consisting of 2 forms of birth control (1 of which must be a male barrier method such as a latex or polyurethane condom) from start of dosing throughout the clinical study period, and for 90 days after the final study drug administration.
 - b. Nonsurgically sterile male participants must not donate sperm at any time from start of dosing until 90 days beyond the administration of study drug.

All Part A and Part B cohorts:

3. Female participants must be nonpregnant and not lactating, or of nonchildbearing potential (either surgically sterilized [e.g. tubal occlusion, hysterectomy, bilateral salpingectomy] or physiologically incapable of becoming pregnant, or postmenopausal with amenorrhea for at least 12 consecutive months). Nonpregnancy will be confirmed for all female participants through a serum pregnancy test at screening and at admission to the CRU and at a final study visit. Follicle-stimulating hormone will be tested at screening for all female participants.

Healthy female participants of child-bearing potential who have a fertile male sexual partner must be willing and able to practice effective contraception from admission to 30 days after the final visit.

Sexually active participants must use a combination of 2 of the following methods of contraception, including at least 1 so-called 'barrier' method:

- a. Hormonal contraceptive (oral, transdermal patches, vaginal or injectable)
- b. Intrauterine device with or without hormones
- c. Condom ('barrier' method)
- d. Diaphragm or cervical cap
- e. Sexual abstinence

Contraceptive requirements do not apply for participants who are exclusively in same-sex relationships.

4. Have a body mass index 18 to 32 kg/m².
5. Have given informed consent prior to any study-specific procedures.
6. Are reliable and willing to make themselves available for the duration of the study and are willing to follow CRU-specific study procedures.
7. Have clinical laboratory test results within normal reference range for the population or CRU, or results with acceptable deviations that are judged not clinically significant by the investigator.

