Modeling of preclinical data in GastroPlus™ suggests that the bioavailability of LY3526318 may increase by approximately 3- to 5-fold when administered with a high-fat meal, relative to administration in the fasted state. Consequently, the 100-mg cohort (females only) was chosen to explore the effect of food administration, considering that even if a 5-fold increase in exposure is observed, it would not exceed the exposure at the maximum planned dose of 1000 mg. The 400-mg dose was chosen because even if there was a 5-fold increase in exposure, it would provide acceptable margins of safety of 5x and 10x for the NOAEL in female rats and monkeys respectively, based on dose multiples. Of note, there were no findings for either female rats or monkeys in the toxicology studies, hence the NOAEL is the maximum administered dose in those studies.

Thus, the proposed doses for both the SAD and MAD portions of the study are anticipated to be in the target engagement dose range, while providing adequate margins of safety to address the study objectives.

6 Study Population

Eligibility of participants for the study will be based on the investigator's judgment on results of screening medical history, physical examination, vital signs, clinical laboratory tests, and electrocardiogram (ECG). The nature of any conditions present at the time of the physical examination and any pre-existing conditions will be documented.

Screening may occur up to 28 days prior to enrollment.

Prospective approval of protocol deviations to recruitment and enrollment criteria, also known as protocol waivers or exemptions, is not permitted.

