6.2 Exclusion Criteria

Participants will be excluded from study enrollment if they meet any of the following criteria at screening, unless otherwise noted:

1. Are currently enrolled in a clinical study involving an investigational product or any other type of medical research judged not to be scientifically or medically compatible with this study.
2. Have previously completed or withdrawn from this study or any other study investigating this study drug.
3. Have a history or presence of medical illness including, but not limited to, any cardiovascular, hepatic, respiratory, hematological, endocrine, psychiatric or neurological disease, convulsions, or any clinically significant laboratory abnormality that, in the judgment of the investigator, indicate a medical problem that would preclude study participation.
4. In the opinion of the investigator are considered to be a danger to themselves, or who have answered "yes" to either Question 4 or Question 5 on Suicidal Ideation portion of the Columbia-Suicide Severity Rating Scale (C-SSRS); or answered yes to any of the suicide-related behaviors on the Suicidal Behavior portion of C-SSRS; and the ideation and behavior occurred within the past 6 months
5. Have an abnormality in the 12-lead ECG that, in the opinion of the investigator, increases the risks associated with participating in the study. In addition, participants with the following findings will be excluded:

- a. confirmed Frederica's corrected QT interval >450 msec for men and >470 msec for women. One repeat ECG may be performed if required.
- 6. Have a history of clinically significant multiple or severe drug allergies or severe posttreatment hypersensitivity reactions, which in the opinion of the investigator may hamper participation in the study.
- 7. Are an investigator or CRU personnel directly affiliated with this study, or are immediate family members of investigator or CRU personnel. Immediate family is defined as a spouse, parent, child or sibling, whether biological or legally adopted.
- 8. Are Eli Lilly and Company (Lilly) employees or contractors or an immediate family member of employees or contractors.
- 9. Show evidence of human immunodeficiency virus (HIV) and/or positive human HIV antibodies, hepatitis C and/or positive hepatitis C antibody, or hepatitis B and/or positive hepatitis B surface antigen.
- 10. Have donated blood of more than 500 mL within the previous month.

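### Inclusion 3 as punctuated admits a lactating woman who has been sterilised, and the six-month clause closing exclusion 4 is ambiguous

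*Protocol*

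**What the plan says.** **Inclusion 3 (Protocol Section 6.1).** The opening sentence is "Female participants must be nonpregnant and not lactating, or of nonchildbearing potential". Nonchildbearing potential is then defined as "either surgically sterilized [e.g. tubal occlusion, hysterectomy, bilateral salpingectomy] or physiologically incapable of becoming pregnant", or postmenopausal. The next sentence says "Nonpregnancy will be confirmed for all female participants through a serum pregnancy test at screening", and again at admission and at a final visit. Contraception rules for women of child-bearing potential follow. Lactation is not mentioned again in Sections 6.1 or 6.2.

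**Exclusion 4 (Protocol Section 6.2).** There are three limbs:

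- investigator opinion, leading by *or* into the ideation limb: "In the opinion of the investigator are considered to be a danger to themselves, or who have answered" yes to C-SSRS ideation Question 4 or 5;
- the ideation limb itself;
- behaviour: "or answered yes to any of the suicide-related behaviors on the Suicidal Behavior portion of C-SSRS".

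After a semicolon comes the time window: "and the ideation and behavior occurred within the past 6 months".

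**How the rules operate.** Section 6.2 opens with "Participants will be excluded from study enrollment if they meet any of the following criteria at screening", so any one exclusion is enough. The opening of Section 6 says that prospective approval of deviations from the entry criteria, "also known as protocol waivers or exemptions, is not permitted".

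**The concern.** These are entry rules for a first-in-human trial in healthy people, for whom Section 3.3 anticipates no benefit. Inclusion 3 appears meant to keep lactating women out, yet its structure lets one group of them in. What is at stake is possible exposure of a nursing infant to a compound not previously given to humans, after up to 14 daily doses in Part B.

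Exclusion 4 uses a window that names ideation and behaviour together, after limbs offered as alternatives. Two people applying the same sentence to the same C-SSRS form could reach opposite decisions. Because waivers are barred, the written text is what formal eligibility is judged against.

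**Working it through.** The plan states no figure to reproduce. The check is to write each criterion as a logical rule and run participant profiles through it.

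**Inclusion 3.** Let P = pregnant, L = lactating, N = nonchildbearing potential.

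- As punctuated: (not P and not L) or N.
- With the universal pregnancy test added: not P and (not L or N).
- With both conditions applied to every woman: not P and not L.

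| P | L | N | As punctuated | Plus pregnancy test | Both apply to all |
|---|---|---|---|---|---|
| no | no | no | meets | meets | meets |
| no | no | yes | meets | meets | meets |
| no | yes | no | fails | fails | fails |
| **no** | **yes** | **yes** | **meets** | **meets** | **fails** |
| yes | no | no | fails | fails | fails |
| yes | no | yes | meets | fails | fails |
| yes | yes | no | fails | fails | fails |
| yes | yes | yes | meets | fails | fails |

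The punctuated rule passes 5 of the 8 profiles. The pregnancy test removes the two pregnant ones, leaving 3. The intended rule would pass 2. The remaining difference is one profile: not pregnant, lactating, nonchildbearing potential. It can occur in practice on the assumption that tubal occlusion or salpingectomy does not stop lactation. She must still meet every other criterion, but none of those names lactation.

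**Exclusion 4.** Let D = judged a danger to self, I = yes to Question 4 or 5, B = yes to any suicidal behaviour, and i6, b6 = ideation, behaviour within six months. Four readings of the closing clause:

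- R1, both required, governing everything: (D or I or B) and (i6 and b6).
- R2, both required, governing the two C-SSRS limbs: D or ((I or B) and (i6 and b6)).
- R3, attached to the behaviour limb only: D or I or (B and i6 and b6).
- R4, each respectively: D or (I and i6) or (B and b6).

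| Profile | R1 | R2 | R3 | R4 |
|---|---|---|---|---|
| Recent ideation only, not judged a danger | not excluded | not excluded | excluded | excluded |
| Recent ideation only, judged a danger | not excluded | excluded | excluded | excluded |
| Recent behaviour only, not judged a danger | not excluded | not excluded | not excluded | excluded |
| Both recent, not judged a danger | excluded | excluded | excluded | excluded |
| Judged a danger, no ideation or behaviour | not excluded | excluded | excluded | excluded |

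Recent ideation alone excludes under two of the four readings. Recent behaviour alone excludes under R4 only.

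**Places for women.** From Table 5-1, Cohorts 2, 3, 4, 5, 6 and 10 plan 4 + 8 + 8 + 8 + 8 + 8 = 44 women. Part B adds 24, giving 68. The planned total is 60 + 24 = 84. So 68 of 84 places are for women, before any in Cohort 1.

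**The case against.** **On inclusion 3**, the intent to bar lactating women is plain, and an investigator taking a medical history could decline such a participant. Participants are also confined: to Day 3 or 4 in Part A and to Day 15, 18 or 19 in Part B, so an infant would be exposed only through milk given or expressed during the stay, or nursing after discharge. The intent is clear, but the sentence does not carry it out, and a discretionary refusal is not a criterion. Confinement narrows the gap without closing it. Discharge falls 48 hours after the dose in Cohorts 1-6, 72 hours in Cohort 10, and 24, 96 and 120 hours after the last dose in Cohorts 7, 8 and 9. Nothing is written about nursing afterwards, and the rationale in Appendix 8 records a half-life longer than predicted.

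**On exclusion 4**, a reader might infer that recent ideation without behaviour does not exclude as written. The documents do not support that as a settled reading. The limbs are joined by *or*; only the closing clause uses *and*, and it can fairly mean each respectively. The strict reading would also let recent suicidal behaviour alone pass, and under R1 would switch off the investigator's opinion. Such results suggest it was not intended. On the other side, R3 is weak, because the clause names ideation and a semicolon separates it from the behaviour limb. The real contest is between requiring both and applying to each.

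There is also partial cover: the investigator-opinion limb (except under R1), exclusion 3 on psychiatric illness, the repeat C-SSRS on Day -1, and the physician evaluation required by Section 9.4.5. Most of this rests on judgment, so it reduces the consequence of the ambiguity without resolving it.

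**Conclusion.** The inclusion 3 point holds on the wording. A lactating woman sterilised by tubal occlusion or salpingectomy meets it, and no other eligibility rule mentions lactation. This assumes that neither procedure stops lactation and that the criterion is applied as punctuated.

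The exclusion 4 point holds only as an ambiguity: if the clause requires both, either recent ideation alone or recent behaviour alone escapes the C-SSRS limbs; if it applies to each, neither does. The further inference that someone with current ideation would be dosed is not supported, because it needs both the strict reading and a failure of every other safeguard.

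The size cannot be estimated. The documents give no frequency for either case, and both are expected to be rare. The 68 of 84 figure counts places for women. It should not be read as the number affected, which for inclusion 3 is limited to women who are both lactating and sterilised by a route that permits lactation. No endpoint, estimate or sample size is touched.

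**What to change.** **Inclusion 3:** require every female participant to be both nonpregnant and not lactating. Then, in a separate sentence, let childbearing status decide only whether the contraception requirement applies, keeping the present list for nonchildbearing potential.

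**Exclusion 4:** the sponsor should confirm what the six-month window is meant to govern and tie it explicitly to each C-SSRS limb. If either event alone is meant to exclude, replacing *and* with *or* between ideation and behaviour in the closing clause would say so. Changing that one word does not show whether the window also governs the investigator-opinion limb, so if it is not meant to, the text should say that too.

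**Cost:** wording changes to two criteria in a protocol amendment. No new procedure, and no change to sample size or analysis. Sections 5.2 and 7.4 allow additional cohorts, so the wording could still apply to later enrolment.

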According to the International Council for Harmonisation (ICH) guidelines ([ICH 2009](#)), women of child-bearing potential (WOCBP) can be included in early clinical trials without nonclinical developmental toxicity studies (e.g. embryo-fetal studies) in certain circumstances. In this study, participants who are WOCBP will receive 2 weeks of treatment while maintaining adherence to highly effective contraception to mitigate the risk of pregnancy.

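### Inclusion criterion 3 lists abstinence among the methods that sexually active women combine in pairs, so a permitted pair can leave only one method in use

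*Protocol*

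**What the plan says.** Protocol Section 5.4 explains why women of child-bearing potential may enter the trial without embryo-fetal studies. The mitigation it names is that "participants who are WOCBP will receive 2 weeks of treatment while maintaining adherence to highly effective contraception to mitigate the risk of pregnancy".

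The rule that the site applies is inclusion criterion 3 in Section 6.1, under the heading "All Part A and Part B cohorts". A woman of child-bearing potential with a fertile male partner "must be willing and able to practice effective contraception from admission to 30 days after the final visit". The criterion continues: "Sexually active participants must use a combination of 2 of the following methods of contraception", and at least one of the two must be a barrier. Five items follow: (a) hormonal, (b) intrauterine device, (c) "Condom ('barrier' method"), (d) diaphragm or cap, and (e) "Sexual abstinence". Only item c carries the barrier label. Women exclusively in same-sex relationships are exempt.

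Criterion 2a, for male participants in the Part A cohorts through 100 mg, is worded differently: "When engaging in sex with a WOCBP, both the male participant and his female partner must use highly effective contraception". It describes this as "highly effective contraception consisting of 2 forms of birth control (1 of which must be a male barrier method".

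**The concern.** Abstinence is a sound way to avoid pregnancy, but only as an alternative to contraception. Criterion 3 puts it on a list from which women who are sexually active pick two. A woman who names condom and abstinence has named a permitted pair. If she then has intercourse, the condom is the only method in use.

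Section 5.4 rests the inclusion of these women on a stronger safeguard than that. Eligibility is judged on criterion 3, so the safeguard is only as good as its wording. What is at stake is avoidable exposure of a pregnancy to a drug that, on Section 5.4's own account, is being given to these women without embryo-fetal studies behind it. Nothing in the estimation of safety or pharmacokinetic endpoints depends on the point.

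**Working it through.** The plan gives no figure to reproduce. The check is a comparison of texts, a count of pairs, and a look at when the rule has work to do.

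**1. Texts side by side.** Section 5.4 says 'highly effective'; criterion 3 says 'effective' but adds two methods with a barrier. No other current text raises criterion 3 to the Section 5.4 wording or bars abstinence from the pair. The Section 5.4 sentence speaks of two weeks of treatment, which is Part B, while criterion 3 covers both parts.

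**2. Permitted pairs.** Let H = hormonal, I = intrauterine device, C = condom, D = diaphragm or cap, A = abstinence. All pairs: 5 × 4 / 2 = 10.

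- Only C is a barrier: HC, IC, CD, CA = 4 permitted. One contains abstinence (CA), so 1 of 4.
- C and D are both barriers: HC, IC, CD, CA, HD, ID, DA = 7 permitted. Two contain abstinence (CA, DA), so 2 of 7.
- With item e removed: 4 − 1 = 3 pairs (HC, IC, CD), or 7 − 2 = 5 pairs (HC, IC, CD, HD, ID). Each is then two methods in actual use.

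**3. When the rule matters.** In Part B, women are confined from Day -1 to Day 15, 18 or 19 (Section 5.1), so confinement covers the dosing days. Two windows remain.

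- Between doses: women in Cohorts 3, 4 and 10 go home and return for another dose. Planned numbers are 8 + 8 + 8 = 24, of whom 6 + 6 + 8 = 20 receive LY3526318. Planned women overall: Cohorts 2 to 6 and 10 give 4 + 8 + 8 + 8 + 8 + 8 = 44; Cohort 1 adds 0 to 8; Part B adds 24; total 68 to 76.
- After final discharge, to 30 days past the final visit (Day 10 in Part A, Day 23 in Part B, before the ±2-day window): Cohorts 1 to 6, (10 − 3) + 30 = 37 days; Cohort 10, (10 − 4) + 30 = 36; Cohort 7, (23 − 15) + 30 = 38; Cohort 8, (23 − 18) + 30 = 35; Cohort 9, (23 − 19) + 30 = 34.

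The headcounts are ceilings. The documents do not say how many women would be of child-bearing potential with a fertile male partner.

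**4. Pregnancy tests.** Criterion 3 schedules serum tests at screening, at admission and at the final visit. Table 2-2 places one at Day -1 of each period in Cohort 10. For Cohorts 3 and 4, the Appendix 5 total of 111 mL equals 11.5 + 7 × 6.5 + 18 × 3. The seven laboratory draws fit Days -1, 2 and 3 in two periods plus one follow-up, so the Day -1 blood draw recurs before the second dose. No test is scheduled in the 30 days after the final visit.

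**The case against.** The strongest reply is that the pair is not really permitted. Criterion 3 requires two methods to be used, and a woman having intercourse is not using abstinence, so she would be in breach. On this view item e is merely misplaced and was probably meant for women who are not sexually active. That is a fair guess at the intent, and it is why the point is minor. It does not remove the defect: the opening words address sexually active participants and ask for a combination, and abstinence is on the list. A site following the text could accept the pair.

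Two further replies stand in full. Criterion 3 asks for more than its adjective suggests, since it already demands two methods with a barrier. And confinement, repeat testing, discontinuation on a positive test in the unit (Section 8) and pregnancy reporting (Section 9.2.1) all limit the consequences. Testing can stop re-dosing of a woman found pregnant, but it cannot prevent the pregnancy.

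A reader might infer that criterion 2a defines 'highly effective' for the whole protocol, so that every pair without a male condom also fails. The documents do not support that. Criterion 2a is written for male participants and their partners, with its own 90-day period, and neither Section 5.4 nor Appendix 1 extends its definition to women who take the drug. Hormonal plus diaphragm and intrauterine device plus diaphragm are both two real methods.

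A reader might also turn the one-week minimum washout into a minimum time at home for Cohorts 3 and 4. Section 7.4.1.1 makes the second dose in Cohort 3 wait for Cohort 4 data, and the second dose in Cohort 4 wait for Cohort 6 data, so the washout alone does not fix that interval.

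**Conclusion.** The point holds as a minor defect in an eligibility rule that protects participants. As written, 1 of 4 permitted pairs (condom as the only barrier) or 2 of 7 (diaphragm or cap also a barrier) leaves a single method in use for a woman who is not abstinent. That is weaker than the mitigation given in Section 5.4. The choice of adjective is the lesser part of the mismatch.

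The counts of pairs describe the wording; they are not estimates of pregnancy risk. The conclusion assumes that the site applies criterion 3 literally and that no instruction outside the protocol and SAP corrects it; the consent text was not available. At most 24 planned women are re-dosed after going home, and the rule runs for 34 to 38 days after final discharge. No endpoint, sample size or analysis changes.

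**What to change.** Amend criterion 3 in four places:

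- Change 'effective' to 'highly effective', to match Section 5.4.
- Delete item e from the methods to be combined.
- State that complete abstinence from admission through 30 days after the final visit is a stand-alone alternative, and that the two-method rule applies if the woman becomes sexually active.
- State whether the diaphragm or cervical cap counts as a barrier method.

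Keep the start and end of the contraception period and the same-sex exemption. Do not add a male-condom requirement for all women: the protocol does not ask for one in this group, and it could exclude candidates who use two other sound methods.

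The cost is a small wording amendment to the protocol and consent form, with no added visits, samples or data fields.
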